7.13.3 CSF Sampling Procedure

Cerebrospinal fluid will be sampled via the device. If this is not possible, and if CSF sampling is necessary, either for adherence to the protocol, or to investigate clinical concerns, an LP may be performed to sample CSF, either with or without administration of drug afterwards.

7.13.4 Device Removal

If at the time of a scheduled dosing it is not possible to administer a full medication dosage as per the standard administration steps detailed in the device's IFU due to a device-related issue, the IDDD will be declared a device malfunction. If the device malfunction is irreversible and cannot be corrected without a device surgical intervention, the IDDD will be declared a device failure, starting from the date of the initial malfunction.

The IDDD will then be surgically removed or revised and a new device and/or device components will be re-implanted at the earliest possible opportunity, preferably at the same time.

Patients who have a PORT-A-CATH IDDD device failure will have this device replaced by a SOPH-A-PORT Mini S.

Details of the device removal will be recorded in the patient's eCRF. Refer to the relevant IFU for further details.

If the IT space is not accessible via the IDDD, study drug may be administered by LP up to 5 times.

Patients will have the IDDD removed when they discontinue from the study, unless the patient is continuing to receive treatment through another mechanism (eg, extension study, expanded access, commercially available).

7.14 Cerebrospinal Fluid Opening Pressure Measurement

A CSF opening pressure measurement (cm of H₂O) will be conducted as per standard hospital practice. The measurement will be obtained whenever a LP is performed and an IDDD revision or replacement is done.

7.15 Dispensing Study Drug

A visual examination of both the port and catheter track will be performed before each IT injection.

HGT-1410 will be administered IT by means of an IDDD (or via LP if necessary) to patients on Day 2 (±2 days) of Week 1 of each treatment month.

The patient may be sedated for this procedure. HGT-1410 will be administered through an appropriately sized syringe (see the Pharmacy Manual). If the IT space is not accessible via the IDDD, HGT-1410 may be administered via LP. See Section 6.3.3 for details.

For the Soph-A-Port Mini S, a 22-gauge Huber non-coring needle is to be used for access to the implanted port; standard hypodermic needles would damage the septum and may cause leakage. If no needle-free connector is present, either a stopcock or the Huber needle infusion set's clamp is to be used to prevent CSF backflow and to mitigate the risk of air entering the system. It is possible to use other brands of Huber non-coring needles, provided that their specifications are identical to that of the Huber needle supplied by Sophysa in the SOPH-A-PORT Mini S (22G).

7.16 Pharmacokinetic Assessments

Pharmacokinetic assessments are not included in this study.

7.17 Neurological Examination

A neurological examination to monitor CNS changes in a patient's neurological status will be conducted during this study. See [Appendix 2](#) for a complete list of the neurological examinations.

The neurological exam should not occur sooner than 4 hours after study drug administration or before the patient has fully recovered from any anesthesia administered for the dosing, whichever occurs later.

7.18 Anti-rhHNS Antibody, Heparan Sulfate, and Heparan Sulfate Derivative Determination

Blood samples will be collected and evaluated at Shire HGT laboratories for the determination of anti-rhHNS antibodies, and plasma and serum heparan sulfate and heparan sulfate derivatives. Samples will be reserved in accordance with local regulations for potential future MPS IIIA research that may determine biomarkers of disease severity and progression.

Two blood samples will be collected from each patient at each designated time point. One sample will be collected in tubes intended for serum specimens, while the second sample will be collected in tubes intended for plasma specimens. Blood sample collection, processing, and shipping instructions will be provided in the Laboratory and/or Study Operations Manual.

7.19 Neurocognitive and Developmental Assessments

Patients will undergo neurocognitive and neurobehavioral development testing. The assessments are estimated to last between 2 and 4 hours and must be conducted prior to sedation or anesthesia.

A full neurodevelopmental assessment, including global development, cognition, adaptive behavior, receptive and expressive language, and gross motor function, will be evaluated using standardized developmental and behavioral tests to provide a surrogate and quantifiable measure of global CNS neurodevelopmental/neurobehavioral function.

All patients will have received a series of standardized neurodevelopment assessments; in the HGT-SAN-055 study, patients in HGT-SAN-067 will continue with the age specific assessment they began with in HGT-SAN-055. If, however, a patient's capability improves and they

become capable of completing assessments at a higher level, any such additional assessments may be added. Any additional assessments would be performed after the original assessments have been carried out.

For this study, outcome measures will be computed for each patient enrolled. The psychometric instruments and Sanfilippo-specific assessments are summarized below in [Table 7-1](#) and [Table 7-2](#), respectively. See [Appendix 2](#) for details on these assessments.

Table 7-1 Neurodevelopmental Assessments Tests

Developmental or Cognitive Domain(s)	Patient Age: Representative Cognitive Test or Scale
COGNITIVE DEVELOPMENT ASSESSMENT	
Summary score and sub-domains: - Cognitive - Motor - Social/emotional	0 to 42 months: Bayley Scales of Infant Development-III Bayley Scales of Infant Development, Third Edition (BSID-III) ²³
- Cognitive - Processing skills	3 to 18 years: Kaufman Assessment Battery for Children, Second Edition (KABC-II) ²⁴
GROSS AND FINE MOTOR SKILLS ASSESSMENT AND VOLUNTARY MOVEMENT	
Motor	3.0 to 16:11 years: Movement Assessment Battery for Children II (MABC-2) ²⁵
- Cognitive - Motor	0 to 5 ½ years: Bayley Scales of Infant Development III (BSID-III) ²³
ADAPTIVE BEHAVIOR	
Communication Daily Living Socialization Motor Skills	0 to 90 years: Vineland Adaptive Behavior Scales (VABS-II) Second Edition ²⁶

Table 7-2 Sanfilippo-Specific Disability Assessment And Behavior Rating Scales

DEVELOPMENTAL OR COGNITIVE DOMAIN(S)	SANFILIPPO SPECIFIC ASSESSMENTS
Parent-scored behavioral inventory - communication: understanding - communication: expression - tantrums - specific behaviors inventory - mood & emotions inventory	Sanfilippo Behavior Rating Scale (SBRS)
MPS-specific disability score - cognitive functioning - expressive language - motor score	Four-Point Scoring System/Total Disability Score (FPSS/TDS) ⁵

7.20 Sleep Questionnaire: Children's Sleep Habits Rating Scale

A sleep questionnaire, Children's Sleep Habits Rating Scale, will be administered to the patient's parent(s)/legally authorized representative(s).

7.21 Age-Dependent, Health-Related Quality of Life in Children

The Quality of Life questionnaires will be administered as outlined in Sections [7.21.1](#), [7.21.2](#), and [7.21.3](#).

7.21.1 Quality of Life Indicator: CHQ-50

The Child Health Questionnaire™ Parent Form 50 Questions (CHQ-50) will be administered during the study. The questionnaire is a generic quality of life instrument, measuring 14 unique physical and psychosocial concepts, which was developed for children from 5 to 18 years of age.

7.21.2 Quality of Life Indicator: CHQ-87

The Child Health Questionnaire™ Child Form 87 (CHQ-87) will be administered during the study. The CHQ-87 is a child and adolescent self-report, developed for ages 10 and older, which assesses the child's self-perceived physical and psychosocial well-being.

7.21.3 Quality of Life Indicator: ITQOL

The Infant Toddler Quality of Life Questionnaire™ (ITQOL) will be administered during the study. The ITQOL was developed for children at least 2 months of age up to 5 years and assesses the physical, mental, and social well being of the child and assesses the quality of the parent/legally authorized representative(s) life.

7.22 Concomitant Medications, Therapies and Medical/Surgical Procedures

All non-protocol treatments that occur from the time of informed consent (and assent, if applicable) through the safety follow-up contact are regarded as concomitant and will be documented on the appropriate pages of the eCRF. Concomitant therapy includes medication (including Genistein), therapies/interventions administered to patients, and medical/surgical procedures performed on the patients.

Every effort should be made to keep symptomatic Sanfilippo syndrome Type A treatment constant throughout the study. However, changes in medications are acceptable if necessary according to clinical judgment. All changes will be recorded on the appropriate eCRF. Concomitant medication will be coded using WHO-DD.

7.23 Adverse Events

7.23.1 Definitions of Adverse Events and Serious Adverse Events

7.23.1.1 Adverse Event

An AE is any noxious, pathologic, or unintended change in anatomical, physiologic, or metabolic function as indicated by physical signs, symptoms, or laboratory changes occurring in any phase of a clinical study, whether or not considered study drug-related. This includes an exacerbation of a pre-existing condition. Once the informed consent is signed and dated, any adverse event prior to the start of study drug must be reported.

AEs include:

- Worsening (change in nature, severity, or frequency) of conditions present at the onset of the study
- Intercurrent illnesses
- Drug interactions
- Events related to or possibly related to concomitant medications
- Abnormal laboratory values (this includes significant shifts from baseline within the range of normal that the Investigator considers to be clinically important)
- Clinically significant abnormalities in physical examination, vital signs, and weight

Throughout the study, the Investigator must record all AEs on the AE eCRF, regardless of the severity or relationship to study drug. The Investigator should treat patients with AEs appropriately and observe them at suitable intervals until the events stabilize or resolve. AEs may be discovered through observation or examination of the patient, questioning of the patient, complaint by the patient, or by abnormal clinical laboratory values.

In addition, AEs may also include laboratory values that become significantly out of range. In the event of an out-of-range value, the laboratory test should be repeated until it returns to normal or can be explained and the patient's safety is not at risk.

All AEs should be recorded with causality assessment.

The information presented below is intended to provide issues to consider for AEs associated with intrathecal injections of HGT-1410. In general, these AEs can be classified as follows:

- Adverse events due to systemic exposure to HGT-1410 caused by the drug diffusion from the CSF to the peripheral circulation;
- Adverse events related to the direct delivery of HGT-1410 to the intrathecal CSF space and meninges, and subsequent diffusion into brain parenchyma, via an intrathecal route
- IDDD-related AEs

Note: the classification of potential AEs and the examples presented below are based on purely theoretical considerations and/or published literature as there is limited human experience with intrathecal HGT-1410 therapy to date.

7.23.1.2 Potential Adverse Events: Intrathecal recombinant human heparan N-sulfatase

ADVERSE EVENTS RELATED TO THE DIRECT DELIVERY OF HGT-1410 TO THE CNS THROUGH INTRATHECAL ADMINISTRATION

Examples of AEs observed in other published clinical trials with intrathecally-administered peptides or proteins, include, but are not limited to the following: headache, fever, feeling of warmth, sensory parathesias (including feelings of warmth, tingling, or pain) or autonomic symptoms such as dry mouth or gustatory abnormalities (including loss of smell and metallic taste). Changes in mental cognitive status or level of consciousness that are not caused by pre-medication may either occur acutely or develop post-injection, over time

ADVERSE EVENTS DUE TO SYSTEMIC EXPOSURE TO HGT-1410

Although HGT-1410 is given intrathecally only, some proportion of the drug will diffuse from the CSF into the peripheral circulation. The resulting systemic exposure may cause events that are typically seen in patients receiving ERT via an intravenous administration, known as infusion-related reactions. An infusion-related reaction is defined as an adverse event that (1) begins either during or within 24 hours after the start of the infusion, and (2) is judged as possibly or probably related to study drug. Other AEs that occur prior to the infusion, along with AEs associated with protocol-defined testing and assessments (laboratory testing and physical examinations) that were performed prior to the infusion will not be defined as infusion-related reactions.

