7.23.3 Classification of Adverse Events and Serious Adverse Events

The National Cancer Institute Common Terminology Criteria for Adverse Events (NCI CTCAE) version 3.0 grading scale should be referenced when assessing the severity of an AE (see [Appendix 6](#)). If an AE is not described in the NCI CTC, the severity should be recorded based on the scale provided in [Table 7-3](#). The severity of all AEs/SAEs should be recorded on the appropriate eCRF page. Adverse events are graded as Grade 1, 2, 3, 4, or 5 corresponding, respectively, to a severity of mild, moderate, severe, life-threatening, or death.

Table 7-3 Adverse Event Severity

Severity	Definition
Grade 1 (Mild)	No limitation of usual activities.
Grade 2 (Moderate)	Some limitation of usual activities.
Grade 3 (Severe)	Inability to carry out usual activities.
Grade 4 (Life-threatening)	Immediate risk of death.
Grade 5 (Death related to an AE)	Death

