7.23.4 Relatedness of Adverse Events and Serious Adverse Events

Relationship of an AE or SAE to investigational product, device, device surgical procedure, or IT administration process is to be determined by the Investigator based on the definitions in [Table 7-4](#):

Table 7-4 Adverse Event Relatedness

Relationship to Product(s)	Definition
Not Related	Unrelated to study drug, device, device surgical procedure, or IT administration process..
Possibly Related	A clinical event or laboratory abnormality with a reasonable time sequence to administration of study drug, device, device surgical procedure, or IT administration process but which could also be explained by concurrent disease or other drugs or chemicals.
Probably Related	A clinical event or laboratory abnormality with a reasonable time sequence to administration of study drug, device, device surgical procedure, or IT administration process unlikely to be attributable to concurrent disease or other drugs and chemicals and which follows a clinically reasonable response on de-challenge. The association of the clinical event or laboratory abnormality must also have some biologic plausibility, at least on theoretical grounds.
Definitely Related	
The event follows a reasonable temporal sequence from administration of the medication, device, device surgical procedure, or IT administration process follows a known or suspected response pattern to the medication, is confirmed by improvement upon stopping the medication (dechallenge) and reappears upon repeated exposure (rechallenge).
 
Note that this is not to be construed as requiring re-exposure of the patient to study drug; however, the determination of definitely related can only be used when recurrence of event is observed.

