7.25 Safety-related Study Stopping Rules

If any patient experiences a life-threatening (Grade 4) adverse event or death which is considered by the sponsor to be possibly, probably, or definitely related to study drug **or the IDDD**, or if 2 or more patients experience a Grade 3 adverse event during the trial that is considered by the sponsor to be possibly, probably, or definitely related to the study drug **or the IDDD**, then the site will be instructed to halt further HGT-1410 administration to all patients and the safety data reviewed. Following a review of safety data, the study will be either:

- Resumed unchanged
- Resumed with modifications to the protocol or
- Terminated

Patient safety will be monitored on a continuous basis during this study until the last patient completes his or her last scheduled study visit/assessment.

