10.6 Efficacy, Safety, and Pharmacodynamic Evaluations

10.6.1 Primary Analyses

10.6.1.1 Safety Analysis

In general, safety assessments will be based on all assessments post-baseline. The assessment of safety will be based primarily on the frequency of AEs, and on the frequency of clinically notable abnormal vital sign and laboratory values. Changes from baseline will be calculated by subtracting the baseline value from the post-baseline value.

All enrolled patients who had an IDDD surgical procedure and/or received administration of HGT-1410 will be included in the safety analysis.

Adverse events will be recorded throughout the study and at early termination. Adverse events and medical conditions will be coded using the Medical Dictionary for Regulatory Activities (MedDRA).

Adverse events will be summarized by presenting, for each dose group, the number and percentage of patients having any AE, having an AE in system organ class, and having each individual AE. In addition, those events which resulted in death or were otherwise classified as serious will be presented in a separate listing. The incidence of treatment-emergent adverse events, defined as all AEs from the time of the surgery for IDDD implantation to the last follow up contact, ie, 30 days after the last HGT-1410 administration, (new or worsened from baseline) will be summarized by system organ class, severity, type of adverse event and relationship to trial medication/procedure.

Treatment-emergent AEs deemed related to HGT-1410 administration will be summarized separately.

IDDD, and procedure-related AEs will be summarized within system organ class by preferred term. IDDD and procedure-related AEs will be tabulated by severity (mild, moderate, severe) and degree of relatedness. Separate tabulations will be provided for adverse events related to the IDDD, device surgical procedure (including post-implant infections) and IT administration process. These summaries will be presented by device and overall, as appropriate.

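### Two safety category sets do not match the protocol's own scales: the infusion-related reaction definition omits definitely related events, and the device/procedure severity breakdown stops at severe

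*Protocol*

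**What the plan says.** All references are to the current protocol text (Amendment 5).

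**Infusion-related reactions.** Section 7.23.1.2 sets two conditions: a time window (onset during the infusion or within 24 hours after its start) and a causality condition, that the event "is judged as possibly or probably related to study drug". The causality scale in section 7.23.4, Table 7-4, has four levels: not, possibly, probably and definitely related. On the last, the table adds that "the determination of definitely related can only be used when recurrence of event is observed". The stopping rule in 7.25 names every related level; its Grade 3 limb refers to events "considered by the sponsor to be possibly, probably, or definitely related to the study drug" or the intrathecal drug delivery device (IDDD).

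**Device and procedure events.** Section 10.6.1.1 states: "IDDD and procedure-related AEs will be tabulated by severity (mild, moderate, severe) and degree of relatedness". Section 7.23.3 states: "Adverse events are graded as Grade 1, 2, 3, 4, or 5 corresponding, respectively, to a severity of mild, moderate, severe, life-threatening, or death". It makes no exception for device events. The stopping rule opens with "If any patient experiences a life-threatening (Grade 4) adverse event or death which is considered" and applies to the IDDD as well as to the drug.

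**The concern.** In both places the protocol fixes a list of categories that is shorter than the scale on which the data are recorded.

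For infusion-related reactions, the missing level is the strongest attribution, and it is reserved for events that have been seen to recur. Dosing is every 28 days for a planned 4 years, so recurrence on a later dose is how a repeated reaction would show itself. An event that becomes eligible for the definite level by recurring would, if rated so, fall outside the definition.

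For device and procedure events, the missing levels are Grade 4 and Grade 5. These are foreseeable. Appendix 3 lists meningitis or encephalitis, spinal cord damage and paralysis among expected device effects, and the CTCAE scale in Appendix 6 places disabling as well as life-threatening events at Grade 4. One such event related to the IDDD could halt dosing under 7.25 and yet have no place in the device severity breakdown.

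Adverse events by type and severity are the first primary endpoint listed in section 3.1, and 10.6.1.1 says the device summaries will be shown by device and overall, as appropriate. That is where the newer port would be set beside the one it replaces.

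**Working it through.** The protocol states no figure to reproduce and no formula applies. The check is a comparison of category sets.

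**Causality**

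| Place in the protocol | Possibly | Probably | Definitely |
|---|---|---|---|
| Table 7-4 (7.23.4), the recording scale | yes | yes | yes |
| 7.25, stopping rule | yes | yes | yes |
| 7.23.1.2, infusion-related reaction | yes | yes | not named |

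The definition covers 2 of 3 related levels. Because 7.25 names all three, the omission is not a convention used throughout the protocol.

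Consequences, step by step:
1. A first occurrence cannot be rated definitely related, since that level needs an observed recurrence. It can be rated possibly or probably related, and then it meets the definition.
2. A recurrence may be rated definitely related if the other conditions in Table 7-4 are met, including improvement when the drug is stopped. Recurrence is necessary for that rating but does not force it.
3. If the recurrence is rated definitely related, it fails the causality condition in 7.23.1.2 as written.
4. Section 10 contains no table or analysis of infusion-related reactions, and the term is not used in the stopping rule (7.25), the removal criteria (7.27) or the serious adverse event reporting rules (7.23.5.1). The effect is on classification and on any summary of reactions produced later.

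**Severity**

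| Place in the protocol | Grade 1 | Grade 2 | Grade 3 | Grade 4 | Grade 5 |
|---|---|---|---|---|---|
| 7.23.3, recording scale | yes | yes | yes | yes | yes |
| 7.25, stopping rule, drug or IDDD | – | – | yes | yes | yes (death) |
| 10.6.1.1, device/procedure breakdown | yes (mild) | yes (moderate) | yes (severe) | not named | not named |

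The breakdown names 3 of 5 grades. The words it uses map to Grades 1 to 3 by the protocol's own key in 7.23.3.

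Where a Grade 4 or 5 device event would still be reported under section 10.6.1.1:
- the IDDD and procedure summary by system organ class and preferred term, which has no severity limit;
- the treatment-emergent summary by severity and by relationship to medication or procedure, which has no three-level cap;
- the separate listing: "those events which resulted in death or were otherwise classified as serious will be presented in a separate listing". Life-threatening events are serious by definition in 7.23.1.4;
- the listings of all safety data.

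For drug-related events, "Treatment-emergent AEs deemed related to HGT-1410 administration will be summarized separately", with no causality level excluded.

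**The case against.** The strongest case against the point is that nothing is lost. The infusion-reaction definition sits in text that 7.23.1.1 introduces as issues to consider and describes as theoretical or literature-based, and no planned analysis uses it. The device severity list is a parenthesis, not a table shell; the analysis plan, which is not shown, may display the higher grades. With at most 12 patients and full listings, a life-threatening or fatal device event would not go unreported.

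Most of this stands, and it sets the size of the point. A reader might infer that the best-attributed reactions and the gravest device events would be absent from the tables meant to show them. The documents do not support that: there is no reaction table to be absent from, and the device events have the other outlets listed above. A reader might also infer that a repeated reaction is automatically moved to the definite level and so drops out. Table 7-4 does not say so, and the protocol prescribes no re-rating of the first event.

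What does not stand is the appeal to the analysis plan. These are not details left open. The protocol states the category sets, and a plan that followed it literally would carry the mismatch forward. Nor does the Amendment 4 change log settle it. Its mention of Grades 1 to 3 in connection with device-associated events is not in current section 7.23.3, and a cap at Grade 3 would sit badly with the Grade 4 IDDD trigger in 7.25.

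**Conclusion.** Both mismatches are present in the current text and hold as internal inconsistencies. Section 7.23.1.2 leaves out one of three related levels, and the device/procedure severity breakdown in 10.6.1.1 leaves out two of five grades. The first affects how events are classified; the second leaves one breakdown with no place for life-threatening or fatal events that are reported elsewhere.

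The two gaps differ in kind and should not be merged into one statement that the most serious category is dropped: definitely related is a level of attribution, not of seriousness. Nor can the effect be put in patients. With at most 12 patients one patient is 1/12 = 8.3%, but that is only the weight of one patient and is not tied to any event that either rule would drop.

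The conclusion assumes that the two lists are read literally. If the analysis plan already uses all related levels and all five grades, only the protocol wording needs correcting. This is a minor consistency correction.

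**What to change.** - **Section 7.23.1.2:** require that the event be judged possibly, probably or definitely related to study drug, the same three levels as in 7.25.
- **Section 10.6.1.1:** tabulate events related to the IDDD, the device surgical procedure and the intrathecal administration process by Grades 1 to 5, as defined in 7.23.3, in place of the three named severities.

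The cost is two wording edits and a check that the analysis plan and its table shells use the same categories. No new data are needed, because causality and grade are already recorded on the full scales, and patient management does not change.
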